### 3.5 MULTIPLICITY ISSUES

All comparisons will be between rilzabrutinib and placebo in the adult ITT population.

[figure not shown]
To control the family-wise type I error, a fixed-sequence procedure will be applied to the primary endpoint and key secondary endpoints at a 2-sided 5% significant level, ie, each hypothesis will be formally tested only if the preceding one is significant at the 5% level (see [Figure 1](#) below).

No multiplicity adjustment will be made on efficacy variables other than those mentioned above.

[figure not shown]

**Figure 1 - Fixed-sequence testing procedure**

**Primary endpoint**

**Key secondary endpoints**

### 3.6 SAFETY ANALYSES

All safety analyses during DB period will be performed on the safety population as defined in [Section 2](#), unless otherwise specified, using the following common rules:

- The analysis of the safety variables will be essentially descriptive, and no testing is planned.
- Adverse events in participants who do not belong to the safety population (eg, exposed but not randomized) will be provided separately.
- Adverse events in participants who did not receive treatment as randomized will be provided separately.

In addition, safety analyses will be performed in the OL and LTE populations during the corresponding treatment periods, as well as on rilzabrutinib safety population across periods (see [Section 2](#), [Section 3.6.2](#), [Section 3.6.3](#)).

#### 3.6.1 Extent of exposure

The extent of IMP exposure will be assessed by the duration of IMP exposure as well as compliance and summarized during each treatment period (safety population for double-blind, open-label population, and LTE population, rilzabrutinib safety population respectively).

##### Duration of IMP exposure

Duration of IMP exposure is defined as last IMP administration date – first IMP administration date + 1 day, regardless of unplanned intermittent discontinuations. If the date of the last dose of IMP is missing, the duration of IMP will be left as missing.

Duration of IMP exposure in days will be summarized quantitatively and categorically during the double-blind period and open-label period respectively: 1 to 28, 29 to 56, 57 to 84, 85 to 112, 113 to 140, 141 to 168, >168 (double-blind period only), afterwards monthly (every 4 weeks) for open-label period and quarterly for LTE period.

Additionally, the cumulative duration of treatment exposure (expressed in participant-years) will be provided.

##### Treatment compliance

A given administration will be considered noncompliant if the participant did not receive the administered doses as required by the protocol.

Percentage of treatment compliance for a participant will be defined as the number of days that the participant was compliant divided by the total number of days that the participant was planned to take.

Treatment compliance will be summarized quantitatively and categorically: <60%, 60% to <80%, 80% to 100%, >100%.

### 3.6.2 Adverse events

#### General common rules for adverse events

All AEs will be graded according to National Cancer Institute Common Terminology Criteria for Adverse Events (NCI-CTCAE version 5.0) and coded to a lower-level term (LLT), preferred term (PT), high-level term (HLT), high-level group term (HLGT), and associated primary system organ class (SOC) using the Medical Dictionary for Regulatory Activities (MedDRA) version currently in effect at Sanofi at the time of database lock.

The AEs will be analyzed in the following 2 categories:

- Pre-treatment AEs: AEs that developed, worsened, or became serious during the pre-treatment period.
- TEAEs: AEs that developed, worsened, or became serious during the treatment-emergent periods ([Section 3.1](#))

The primary focus of AE reporting will be on TEAEs. Pre-treatment AEs will be described separately.

An AE with incomplete or missing date/time of onset (occurrence, worsening, or becoming serious) will be classified as a TEAE unless there is definitive information to determine it is a pre-treatment AE.

If the assessment of the relationship to IMP is missing for an AE, this AE will be assumed as related to IMP. If the severity/grade is missing for 1 of the treatment-emergent occurrences of an AE, the severity/grade will be imputed (by treatment-emergent period) with the maximal severity/grade of the other occurrences. If the severity is missing for all the occurrences, the severity/grade will be left as missing.

Multiple occurrences of the same event in the same participant will be counted only once in the tables within an observation period, using the maximum (worst) grade (by treatment-emergent period). Summaries will be provided for all grades combined unless otherwise specified. Missing grades, if any, will be included in the “all grades” category.

The AE tables will be sorted as indicated in [Table 6](#).

**Table 6 - Sorting of AE tables**

AE presentation	Sorting rules
SOC and PT	By the internationally agreed SOC order and decreasing frequency of PTs a, b
PT	By decreasing frequency of PTs a

a Sorting will be based on the SAR444671/rilzabrutinib intervention group.

b The table of all TEAEs presented by SOC and PT will define the presentation order for all other tables (eg, treatment-emergent SAE) presented by SOC and PT, unless otherwise specified.

### **Analysis of all adverse events**

The overview of TEAE with the details below will be generated:

- Any TEAE
- Any CTCAE Grade  $\geq 3$  TEAE
- Any treatment emergent serious adverse event (SAE)
- Any treatment emergent SAE related to IMP as per investigator's judgement
- TEAE leading to death
- Grade 5 TEAE
- Any TEAE leading to permanent discontinuation of study intervention
- Any TEAE related to IMP as per investigator's judgement
- Any treatment emergent AESI increase in alanine transaminase (ALT)  $>3 \times \text{ULN}$  (Table 8)
- Any  $\geq$ Grade 2 treatment-emergent bleeding events (criteria in Table 8)
- Any  $\geq$ Grade 2 treatment-emergent bleeding events related to IMP as per investigator's judgement
- Any  $\geq$ Grade 2 treatment-emergent infections (criteria in Table 8)
- Any  $\geq$ Grade 2 treatment-emergent infections related to IMP as per investigator's judgement
- Any  $\geq$ Grade 2 treatment-emergent gastrointestinal events (criteria in Table 8)
- Any  $\geq$ Grade 2 treatment-emergent gastrointestinal events related to IMP as per investigator's judgement

The AE summaries in Table 7 will be generated with number (%) of participants experiencing at least one event. TEAE will be provided for each period respectively as specified.

The all TEAE summary by Primary SOC and PT (and other safety summaries (eg, SAEs, deaths), if deemed needed after TEAE evaluation) will be performed by trial impact (disruption) due to COVID-19.

**Table 7 - Analyses of adverse events**

MedDRA levels		DB 12W		DB 24W		OL d	LTE e	DB+OL+LTE f
		Adults	Peds	Adults	Peds	Adults and Peds Separately		
All TEAE	Overview a	✓	✓	✓	✓	✓	✓	✓
	Primary SOC and PT	✓	✓	✓ g	✓ g	✓	✓	✓
	PT			✓				
Common TEAE (≥5% in rilzabrutinib group)	Primary SOC and PT			✓				
	Primary SOC, and PT	✓	✓	✓	✓	✓	✓	✓
	Primary SOC and PT			✓	✓			
TEAE related to IMP as per Investigator's judgment	Primary SOC and PT	✓	✓	✓	✓	✓	✓	✓
TEAE by maximal CTCAE grade	Primary SOC and PT			✓	✓			
Any ≥Grade 3 TEAE	Primary SOC and PT			✓	✓			
Any ≥Grade 3 TEAE related to IMP as per Investigator's judgment	Primary SOC and PT	✓	✓					
Treatment emergent SAE	Primary SOC and PT			✓	✓	✓	✓	✓
Treatment emergent SAE related to IMP as per Investigator's judgment	Primary SOC and PT			✓	✓	✓	✓	✓
TEAE leading to permanent discontinuation of study intervention	Primary SOC and PT			✓	✓	✓	✓	
TEAE leading to death	Primary SOC and PT			✓				✓
Any treatment emergent AESI	PT			✓	✓	✓	✓	

	MedDRA levels	DB 12W		DB 24W		OL d	LTE e	DB+OL+LTE f
		Adults	Peds	Adults	Peds	Adults and Peds Separately		
Any ≥Grade 2 treatment-emergent bleeding event b	PT			✓	✓	✓	✓	
Any ≥Grade 2 treatment-emergent bleeding event b related to IMP as per Investigator's judgement	PT			✓	✓	✓	✓	
Any ≥Grade 2 TEAEs under SOC "Infections and Infestations"	PT			✓	✓	✓	✓	
Any ≥Grade 2 TEAEs under SOC "Infections and Infestations" related to IMP as per Investigator's judgement	PT			✓	✓	✓	✓	
Neutropenia b	PT			✓	✓	✓	✓	
Anemia b	PT			✓	✓	✓	✓	
Thromboembolic events b	PT			✓	✓	✓	✓	
GI events b (analyses below within Section 3.6.2 )	HLT and PT			✓	✓	✓	✓	✓
Covid-19 related TEAEs c	Primary SOC and PT			✓				
Any TEAE by age group (<65, ≥65 years)	Primary SOC and PT			✓				✓
Any TEAE by sex (male, female)	Primary SOC and PT			✓	✓			✓
Any TEAE by concomitant ITP medications (CS, TPO-RA, Both CS and TPO-RA, Neither CS nor TOP-RA)	Primary SOC and PT			✓	✓			✓

MedDRA levels		DB 12W		DB 24W		OL d	LTE e	DB+OL+LTE f
		Adults	Peds	Adults	Peds	Adults and Peds Separately		
Pre-treatment AE	Overview a			✓				
	Primary SOC and PT			✓	✓			
Post-treatment AE	Primary SOC and PT							✓

a Will include the following AE categories: any AEs, any serious AEs, any AEs leading to death, any AEs leading to permanent intervention discontinuation.

b Selection criteria in [Table 8](#).

c Covid-19 related AEs identified by narrow search of SMQ = COVID-19, #20000237.

d Cumulative data from 1st dose of rilzabrutinib during OL period. Adult and pediatric populations separately.

e Cumulative data from 1st dose of rilzabrutinib during LTE period. Adult and pediatric populations separately.

f Cumulative data from 1st dose of rilzabrutinib regardless of period. Adult and pediatric populations separately.

g Including number (percent) of participants with events, number of events and event rate per participant-years of exposure.

DB = double-blind period ; OL = open-label period ; LTE = long-term extension. 12W = 12-week double-blind period ; 24W = 24-week double-blind period;

AE = adverse event ; TEAE = treatment emergent adverse event ; SAE = serious adverse event ; AESI = adverse event of special interest ; GI = gastrointestinal.

SOC = system organ class ; HLT = high level term ; PT = preferred term. CTCAE = common terminology for adverse events.

CS = corticosteroids ; TPO-RA = Thrombopoietin receptor agonist ; CMQ = Customized MedDRA query; SMQ = Standardized MedDRA query.

## **Analysis of deaths**

In addition to the analyses of deaths included in [Table 6](#) the number (%) of participants in the following categories will be provided as appropriate:

- Deaths will be summarized by primary cause of death and treatment period.
  - Death on-study: deaths occurring during the on-study observation period (ie, up to the end of the study)
    - a) Death on-treatment: deaths occurring during the on-treatment period (double-blind, open-label, long-term extension, respectively, [Section 3.1](#))
    - b) Death post-treatment: deaths occurring during the post-treatment period ([Section 3.1](#))
  - Death post-study: deaths occurring after the end of the study

Note: End of the study is the last scheduled visit for those who completed the study, the end-of-study visit date, or the “Completion/Early Withdrawal Date” of the latest period (DB, OL, LTE), whichever later. If death is the end-of-study reason, date of death will be used.

- Deaths in non-randomized participants or randomized but not treated participants

## **Analysis of adverse events of special interest (AESIs) and other AEs of interest**

Adverse events of special interest (AESIs) and other AEs of interest will be selected for analyses as indicated in [Table 8](#). Number (%) of participants experiencing at least one treatment emergent event by PT will be provided for each event of interest during the treatment emergent period ([Section 3.1](#), [Table 7](#)). Tables will be sorted as indicated in [Table 6](#).

**Table 8 - Selections for AESIs and other AEs of interest**

AESIs and other AEs of interest	Selection
Pregnancy	e-CRF “Adverse Events”, AE category=“Pregnancy”, AESI checked yes
Symptomatic overdose (serious or nonserious) with IMP	e-CRF “Adverse Events”, AE category=“Overdose”, AESI checked yes (complementary e-CRF “Overdose”, “Overdose of Rilzabrutinib” checked yes, “Symptomatic Overdose” checked yes)
Increase in alanine transaminase (ALT) >3 × ULN	e-CRF “Adverse Events”, AE category=“ALT increase”, AESI checked yes (Complementary e-CRFs “ALT Increase – Associated Signs and Symptoms” and “ALT Increase – Trigger Factors”)
Infection: Grade 4 or 5 infection where the participant is hospitalized ≥24 h and/or requires emergency care and/or requires IV antibiotics.	e-CRF “Adverse Events”, AE category=“Infection”, AESI checked yes (complementary e-CRF “Infection event form”)
Infection	SOC “Infections and Infestations”

AESIs and other AEs of interest	Selection
Bleeding event	SMQ = Haemorrhages, #20000038, broad and narrow search
Neutropenia	CMQ10801 based on the list of PTs in Section 5.8 a
Anemia	SMQ = Haematopoietic erythropenia, #20000029, broad and narrow search
Thromboembolic events	SMQ = Embolic and thrombotic events, #20000081, broad and narrow search
Gastrointestinal events	HLT "Diarrhoea (excl infective)", "Nausea and vomiting symptoms"

a The list of terms may be adjusted according to MedDRA version changes.  
eCRF = electronic case report form. SMQ = Standardized MedDRA queries. CMQ = customized MedDRA queries. HLT = high level term.

For treatment emergent infection ( $\geq$  Grade 2), bleeding ( $\geq$  Grade 2), and gastrointestinal events, the following analyses will be presented, in addition to those specified in [Table 7](#).

- n (%) of participants with any TEAE, treatment emergent SAE, TEAE leading to death, TEAE leading to permanent study intervention discontinuation, TEAE related to IMP.

#### **Analysis of gastrointestinal events for each PT (ie, nausea, vomiting and diarrhoea, respectively)**

- Maximal CTCAE grade: Grades 1 to 5
- Worst outcome (from most to least severe): Fatal, Not Recovered/Not Resolved, Recovering/Resolving, Recovered/Resolved with sequelae, Recovered/Resolved, Unknown
- Time to first onset in days: mean (SD), median, min, max
- Incidence rate
  - Frequency of events (ie, incidence) by interval of onset:  $\leq 1$  week,  $>1$  to 2 weeks,  $>2$  to 4 weeks,  $>4$  to 8 weeks,  $>8$  to 12 weeks,  $>12$  to 16 weeks,  $>16$  to 20 weeks,  $>20$  to 24 weeks, and  $>24$  weeks. The numerator is the number of participants with an occurrence of the event in the given interval. The denominator is the number of participants exposed at the beginning of the interval. Multiple occurrences of the same event for a participants can be counted in several intervals, but only once in the same interval.
  - Kaplan-Meier estimate of cumulative incidence rate at the end of Weeks 1, 2, 4, 8, 12, 16, 20, 24.
- Average duration of TEAEs
  - Average duration of TEAEs in days (ie, average duration across all resolved occurrences): mean (SD), median, min, max
  - Average duration by interval: 0 to 2 days,  $>2$  to 7 days,  $>7$  days to 1 month,  $>1$  month to 4 months,  $>4$  months

- Cumulative duration of TEAEs
  - Cumulative duration of TEAEs in days (total duration of events over time): mean (SD), median, min, max
  - Cumulative duration by interval: 0 to 2 days, >2 to 7 days, >7 days to 1 month, >1 month to 4 months, >4 months

Kalan-Meier curves will be provided for the time to each GI event (ie, nausea, vomiting and diarrhoea, respectively), as well as for the time to IMP discontinuation due to any GI events. Participants without any event will be censored at the end of the treatment-emergent period.

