### ***Observation period***

The observation period will be divided into 3 segments:

- The **pre-treatment period** is defined as the period up to first double-blind IMP administration.
- **Double-blinded (DB) period**
  - The DB on-treatment period is defined as the period from the first DB IMP administration to the last DB IMP administration + 1 day for participants who did not enter the OL period or to the first OL IMP (the first OL visit is the nominal protocol visit Week 25) for participants who entered the OL period.
  - The DB post-treatment period is defined as the period after the DB on-treatment period for participants who did not enter the OL period.
- **Open-Label (OL) period**
  - The OL on-treatment period is defined as the period from the end of the DB on-treatment period to the last OL IMP administration + 1 day for participants who did not enter the LTE period or to the first OL IMP during the LTE (the first LTE visit is the nominal protocol visit Week 53) for participants who entered the LTE period.
  - The OL post-treatment period is defined as the period after the OL on-treatment period for participants who did not enter the LTE period.
- **Long-term extension (LTE)**
  - The LTE on-treatment period is defined as the period from the end of OL on-treatment period to the last IMP administration + 1 day.

- The LTE post-treatment period is defined as the period after the LTE on-treatment period to the end of study.

Note: Per protocol, the end of study visit occurs 4 weeks post last dose of IMP during the DB, OL or LTE period, whichever later.

Events occurred after the first double-blind IMP administration are considered treatment emergent, including on- and post-treatment events, as defined above. That is, **double-blind treatment-emergent period** includes double-blind on- and post-treatment period. **Open label treatment-emergent period** and **LTE treatment-emergent period** are defined similarly. For rilzabrutinib safety population, the entire treatment-emergent period will start from the 1st administration of rilzabrutinib.

For safety analysis, the 12-week double-blind treatment emergent period is the double-blind treatment emergent period for those discontinued before Week 13 (Day 85) or the period from the first double-blinded IMP administration to the visit date of Week 13 otherwise.

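### GI incidence by interval and the double-blind all-TEAE event rate count off-drug follow-up events over denominators limited to exposure

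*SAP*

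**What the plan says.** **Events.** SAP 3.6.2 defines TEAEs as "AEs that developed, worsened, or became serious during the treatment-emergent periods". Under Observation period in SAP 3.1, the double-blind treatment-emergent period "includes double-blind on- and post-treatment period". The off-drug part belongs to one group only: "The DB post-treatment period is defined as the period after the DB on-treatment period for participants who did not enter the OL period". Its length follows from the note there: "Per protocol, the end of study visit occurs 4 weeks post last dose of IMP". Protocol 4.1.4 records AEs at that visit.

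**GI table by interval.** The SAP says "The numerator is the number of participants with an occurrence of the event in the given interval", and then "The denominator is the number of participants exposed at the beginning of the interval". Neither sentence limits the numerator to on-treatment events or to participants in the denominator.

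**Event rate.** Footnote g of Table 7 sits on one row, all TEAEs by SOC and PT, in the double-blind 24-week columns for adults and pediatrics. It reads "Including number (percent) of participants with events, number of events and event rate per participant-years of exposure". SAP 3.6.1 measures exposure from first to last dose, ignoring temporary interruptions.

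**GI Kaplan-Meier curves.** In the same GI block, participants without an event are censored at the end of the treatment-emergent period. Their risk set therefore includes the follow-up.

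**The concern.** An incidence needs events and people, or time, from the same window. Here the events come from a window that runs past the last dose for some participants, while the people or time come from a window that stops at it. The interval figures are then not the proportion of any defined group who had the event, and the GI table and the GI curves in the same block rest on different risk sets.

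This matters because Protocol 2.4.1 names GI events as the most common treatment-related AEs, so these outputs describe the drug's main known tolerability issue. Week 13 is also a planned exit point: under Protocol section 4, non-responders may leave the study or move to open label. The group still exposed just after Week 12 may be small, and a few off-drug events could then move the reported figure visibly.

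**Working it through.** The plan states no GI interval incidence, no event rate and no exit fractions, so there is no figure to reproduce. The check has two parts.

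**1. One record, read literally.** A participant takes the last blinded dose on Day 80 and does not enter open label. Follow-up runs to about Day 108 (80 + 28). Diarrhoea starts on Day 90.
- Day 90 is in the treatment-emergent period, so the event is a TEAE.
- The >12 to 16 week interval covers Days 85 to 112, so the event is in that numerator.
- Dosing had ended by Day 85, so the participant is not in that denominator.
- For footnote g, the event counts, but exposure stops at 80 days.

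**2. Size, under stated assumptions.** Let w be the share leaving the study at Week 12 without open label, o the share entering open label then, and r the ratio of off-drug to on-drug event rate. Everyone else is treated for 24 weeks and then enters open label. Leavers are taken as no longer exposed when the >12 to 16 week interval starts. The documents give none of w, o or r.

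Relative excess over on-drug events divided by on-drug denominator:
- Interval >12 to 16 weeks: w·r / (1 − w − o)
- Footnote g rate: 4·w·r / [12(w + o) + 24(1 − w − o)]

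Example with w = 0.10, o = 0.30, r = 1:
- Interval: 0.10 / 0.60 = 16.7%.
- Rate: 0.40 / (4.8 + 14.4) = 0.40 / 19.2 = 2.1%.

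Ranges for o = 0.3 or 0.6 and r = 0.25 to 1:

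| w | Interval >12 to 16 weeks | Footnote g rate |
|---|---|---|
| 0 | 0% | 0% |
| 0.05 | 1.9-14.3% | 0.25-1.2% |
| 0.10 | 4.2-33.3% | 0.5-2.6% |
| 0.20 | 10-100% | 1.1-5.6% |

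If the comparison is instead with the same events over a denominator that includes the follow-up, r drops out. At w = 0.10 the interval excess is then 16.7% (o = 0.3) or 33.3% (o = 0.6), and the rate excess is 2.1% or 2.6%.

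In counts, assume a 5% event risk per four weeks and r = 1:
- 129 participants, w = 0.10, o = 0.30: 77.4 exposed and 12.9 in follow-up, so (3.87 + 0.645) / 77.4 = 5.83% against 5.00%.
- 65 participants, w = 0.10, o = 0.60: 19.5 exposed and 6.5 in follow-up, so (0.975 + 0.325) / 19.5 = 6.67% against 5.00%.
- 65 participants, w = 0, o = 0.70: 0.975 / 19.5 = 5.00%, with no excess.

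**Which intervals.** Follow-up after a Day 84 last dose ends at Day 112 (84 + 28), the end of Week 16, so Week 13 leavers affect essentially one interval. The other exposed place is >24 weeks, which starts at Day 169, the target day of the Week 25 visit. Someone who finishes blinded dosing on Day 168 and declines open label is followed to about Day 196, all of it in that interval. Few participants can still be on blinded drug at its start.

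**The case against.** **The term exposed is not defined for this table.** If it was meant to cover follow-up, the interval mismatch disappears. That is fair, but SAP 3.6.1 ties exposure to dosing dates, and the intended reading would still have to be written down.

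**The net direction is not fixed.** The Week 13 visit falls on Day 85 ± 3. Someone dosed to Day 86 to 88 is in the >12 to 16 week denominator although their double-blind period may end within days. If visits were spread evenly over the window, about 3/7 of exits would be in it. With 30% staying blinded and 10% of exits going to follow-up, as-written over true incidence at equal hazard is (0.30 + 0.07) / (0.30 + 0.30) = 0.62, an understatement. This stands. The mismatch only adds events, but the whole interval figure may still be too low.

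**A reader might infer that placebo is inflated more, hiding a GI excess on rilzabrutinib.** SAP 3.2.3.2 does expect high dropout, particularly on placebo. But exits into open label add no double-blind off-drug time, and the documents do not split exits by route and arm. The inference is not supported.

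**A reader might infer that TEAE figures in general are overstated.** They are not. The n (%) tables have no such mismatch, and footnote g covers a single row.

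**A reader might infer that a missing last-dose date deletes a participant's time but keeps the events**, from "If the date of the last dose of IMP is missing, the duration of IMP will be left as missing". SAP 3.8 treats such participants as exposed up to the cut-off date in every analysis before the final one, and the adult double-blind analysis is Step 1 of Table 10. The inference fails there.

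**A matched GI analysis is already planned, and safety is descriptive.** Both are true. They limit the consequence but do not make the interval table or the footnote g rate correct.

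**Conclusion.** The rule is wrong as written. In the GI interval table and the footnote g rate, numerator and denominator cover different person-time. The mismatch adds events without matching denominator whenever someone leaves the study without open label and has an event in follow-up. An off-drug event in the same interval as the last dose causes no mismatch in the interval table if that participant was exposed at its start.

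The size cannot be fixed from the documents. It is zero if all exits enter open label. In the >12 to 16 week interval it can be material: 4-33% relative if 10% leave, over the assumed ranges. The >24 week interval is also vulnerable because its exposed group may be very small. For the footnote g rate it is about 0-6%. That range takes all 24-week completers into open label; any who decline would add to it.

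Neither an arm ranking nor a direction of between-arm bias can be stated. No hypothesis test is affected. The correction is worth making because the tables would otherwise be programmed to a definition that does not give an incidence.

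**What to change.** Match the periods, in one of two ways:

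1. **On-treatment basis.** Restrict the GI interval and footnote g numerators to events up to the last blinded dose + 1 day, or to the first open-label dose for those who enter open label. Keep the exposure denominators.
2. **Treatment-emergent basis.** Keep the numerators. Divide the interval counts by participants still in the treatment-emergent period at the start of the interval. Divide footnote g events by treatment-emergent time: first dose to first open-label dose, or to the end-of-study visit.

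The second agrees with the censoring of the GI curves. Whichever is chosen, define exposed in the GI block and state the time base in footnote g. Table 7 also schedules the GI analyses for open label and the extension, so the wording should cover those versions.

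The cost is SAP wording and one derived variable, with no new data.

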2.4.1. Safety

As of the data cut-off date of 22 April 2021, in 8 completed Phase 1 studies and 4 ongoing Phase 1 studies (more than 280 healthy volunteers), the completed Phase 2 study in participants with pemphigus (41 participants, PRN1008-005), and ongoing Phase 1/2 studies in ITP (61 participants, PRN1008-010), and IgG4 (4 participants, PRN1008-017), rilzabrutinib demonstrated a safety profile characterized by predominantly mild-to-moderate adverse events (AEs) such as GI disturbance and headache, no rilzabrutinib-related deaths, and no evidence of increased risk of infections. There have been no related thrombotic or major bleeding events in the clinical experience with rilzabrutinib to date. In addition, there are no patterns or clinically significant findings from physical examinations, laboratory parameters, electrocardiograms (ECG), or vital signs in healthy-volunteers and in participants from studies conducted to date.

The most common treatment-related AEs as of 22 April 2021 were GI in nature, including nausea, vomiting, and diarrhea. The majority of treatment-emergent adverse events (TEAEs) were mild to moderate in severity. There was 1 serious adverse event (SAE) in Study PRN1008-005 that was assessed by the Sponsor as related to the study drug (cellulitis). Safety and efficacy findings of Study PRN1008-010 (main treatment periods) and LTE-Part A interim analysis were published ([Kuter et al 2022](#), [Cooper et al 2023](#), [Kuter et al 2024](#)). Please refer to the most recent version of the IB for updated safety information.

The marketed BTK inhibitor, ibrutinib, has been studied in combination with rituximab in the treatment of chronic lymphocytic leukemia without published evidence of increased drug-related

AEs ([Burger 2019](#)). There is no a priori drug interaction potential between anti-CD20 biologic drugs and the small molecule rilzabrutinib.

PRN1008-010 (Part A and Part B) study results demonstrated a rapid and sustained platelet response in patients with primary ITP who failed multiple prior therapies and showed a favorable safety profile (Kuter et al 2022, Cooper et al 2023). For summary of overall benefit/risk assessment, refer to [Section 2.7](#).

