9.3.9.3. Follow-up of AEs and SAEs

After the initial AE/AESI/SAE report, the Investigator is required to proactively follow each participant at subsequent visits/contacts. At the pre-specified study end-date, all SAEs, and other AEs, will be followed until resolution, stabilization, the event is otherwise explained, or the participant is lost to follow-up (as defined in Section 7.5.3). Further information on follow-up procedures is provided in [Appendix 12](#).

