- AEs occurring, worsening or becoming serious after the cut-off date will not be included in the analyses. However, any available outcome before database lock, regardless of timing in relation to the cut-off date, of an AE starting prior to the cut-off date will be taken into account. Medications, intervention discontinuations/completions and deaths occurring after the cut-off date will not be included in the analyses.

An independent Data Monitoring Committee (DMC) is used to monitor and assess the safety of participants from this trial through periodic review of the accumulated safety data provided by an independent statistical group. Related details are provided in separate documents (DMC charter).

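### The average duration of nausea, vomiting and diarrhoea counts resolved occurrences only, so it leans short by an unknown amount

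*SAP*

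**What the plan says.** SAP 3.6.2 has a separate list of analyses for nausea, vomiting and diarrhoea, each by preferred term. Four items matter here.

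- **Average duration:** "Average duration of TEAEs in days (ie, average duration across all resolved occurrences): mean (SD), median, min, max". A table by interval follows, with a top category of more than 4 months.
- **Cumulative duration:** "Cumulative duration of TEAEs in days (total duration of events over time): mean (SD), median, min, max", with its own interval table. It is not limited to resolved occurrences, but no end date is given for an event that is still ongoing.
- **Worst outcome:** "Worst outcome (from most to least severe): Fatal, Not Recovered/Not Resolved, Recovering/Resolving, Recovered/Resolved with sequelae, Recovered/Resolved, Unknown".
- **Kaplan-Meier:** planned for time to each GI event and for time to IMP discontinuation due to any GI event, with event-free participants censored at the end of the treatment-emergent period. None is planned for time to resolution.

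On follow-up, Protocol 9.3.9.3 says "all SAEs, and other AEs, will be followed until resolution, stabilization, the event is otherwise explained". SAP 3.8 ends the treatment-emergent period at the cut-off for participants still on treatment. For AEs that began before the cut-off it uses "any available outcome before database lock, regardless of timing in relation to the cut-off date". SAP Table 7 schedules the GI tables for the double-blind, open-label and LTE periods and cumulatively.

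**The concern.** The rule selects on the quantity being measured. For a given onset and follow-up, the longer an occurrence lasts, the more likely it is to be unresolved and left out. A participant whose only diarrhoea never resolves adds nothing to the average.

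Some unresolved events are to be expected. The worst-outcome list has categories for them, follow-up may end at stabilization rather than resolution, and the registration analysis is run at a cut-off while participants are still on treatment.

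The subject is not peripheral. Protocol 2.4.1 states: "The most common treatment-related AEs as of 22 April 2021 were GI in nature, including nausea, vomiting, and diarrhea". For an oral drug taken long term, how long these events last is part of the tolerability picture, and a figure that leans short could mislead a reader of the study report.

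**Working it through.** The plan states no GI duration and no unresolved share, so there is no figure of its own to reproduce. All durations below are assumptions.

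**Closed form.** For an exponential duration with mean m and follow-up F after onset:

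- share unresolved: q = exp(−F/m)
- mean of resolved occurrences: m − F·q/(1 − q)
- mean of observed time, counting ongoing time to date: m·(1 − q)

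Assume a share w of persistent events (m = 120 days), the rest short (m = 5 days, essentially all resolved), and onset spread over the first 28 days, so day 14 on average. If observation stops at day 168, F = 168 − 14 = 154. For persistent events:

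- q = exp(−154/120) = 0.277
- resolved mean = 120 − 154 × 0.277/0.723 = 61.0 days
- observed mean = 120 × 0.723 = 86.7 days

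With w = 10%:

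- resolved-only mean = (0.10 × 0.723 × 61.0 + 0.90 × 5)/(0.10 × 0.723 + 0.90) = 8.91/0.972 = 9.2 days
- observed mean = 0.10 × 86.7 + 0.90 × 5 = 13.2 days
- shortfall = 1 − 9.16/13.17 = 30%

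The same formulas with longer observation give the shortfall against observed time:

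| Observation to | F (days) | Persistent events unresolved | w = 5% | w = 10% | w = 20% |
|---|---|---|---|---|---|
| Day 168 | 154 | 28% | 22% | 30% | 36% |
| Day 280 | 266 | 11% | 14% | 18% | 21% |
| Day 364 | 350 | 5% | 9% | 11% | 13% |

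Against the full mean (w = 10%: 0.10 × 120 + 0.90 × 5 = 16.5 days) the day-168 shortfall is 1 − 9.16/16.5 = 44%.

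**Simulation.** 400,000 events per scenario; onset uniform over 168 days or early (exponential, mean 14 days); observation to day 168 or day 196. The resolved-only mean as a fraction of the true mean was:

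| Duration model | True mean (days) | Fraction of true mean |
|---|---|---|
| Exponential | 5 | 0.97 to 1.00 |
| Exponential | 14 | 0.91 to 1.00 |
| Exponential | 30 | 0.79 to 0.98 |
| Exponential | 60 | 0.59 to 0.84 |
| Exponential | 120 | 0.37 to 0.57 |
| Lognormal | 14 | 0.65 to 0.84 |
| Lognormal | 60 | 0.36 to 0.54 |

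The fraction never exceeded 1. A Kaplan-Meier median with unresolved events censored was within 0.3 days of the true median in every scenario.

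**Which events are omitted.** With uniform onset, observation to day 168 and an exponential mean of 14 days, 8.3% of events were unresolved and had been observed for 14.1 days on average. They are partly late starters. An exponential duration has no memory, so their expected full length is 14.1 + 14 = 28.1 days, twice the mean. The omitted events are preferentially long, but not simply the longest.

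**The case against.** The strongest defence is that the same list already deals with unresolved events. The worst-outcome table shows how many participants have them, and the cumulative duration has no resolved-only restriction and its own interval table. Follow-up to resolution or stabilization, and the use of outcomes known before database lock, reduce the number unresolved. Many adults will be well past their own Week 24 when the last adult reaches it, so stopping every event at day 168 is close to a worst case for those who continue. The safety analysis is descriptive with no testing, and the resolved-only restriction is stated openly.

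Much of this stands. It narrows the point and lowers the plausible size. It does not remove the bias from the average itself. The worst-outcome table has no time in it. The cumulative duration is a total over a participant's events, not a per-event length, and it cannot be computed for an ongoing event without an end date. Stabilization can end follow-up of a chronic event that never resolves. The SAP also shows the alternative elsewhere: its liver analysis (3.6.3.1) keeps cases that never returned, or had not yet returned, to baseline status as categories of their own.

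A reader might infer that the longest-lasting events are dropped. The text does not say that. Long events that resolve stay in, as the top interval shows, and an unresolved event may only have begun late.

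**Conclusion.** The point holds as a bias of known direction and unknown size in one descriptive summary and its interval table. If events are short (exponential mean 14 days or less) the mean is low by 0 to 9%. If a share persists, or durations are long or strongly skewed, it is low by roughly 10 to 40% or more, and less as follow-up lengthens. These figures rest on assumed durations, onset patterns and observation times, none of which is in the documents.

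The median is less sensitive in the mixture scenarios. Even at day 168 with 20% persistent events, only 0.20 × 0.277 = 5.5% of all occurrences are omitted.

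Three stronger readings are not supported. A reader might take the day-168 shortfall of 22 to 36% as an estimate for this trial, but it depends on invented durations and on a stop date that the follow-up and database-lock rules extend for many participants. A reader might conclude that unresolved GI events vanish from the report, but the worst-outcome table counts them. A reader might suspect a distorted comparison between arms, but nothing in the documents shows the bias to differ by arm.

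**What to change.** In the GI list of SAP 3.6.2:

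1. Add Kaplan-Meier time to resolution for each preferred term, with median and quartiles. Censor unresolved occurrences at the end of the treatment-emergent period or the cut-off. SAP 3.8 takes outcomes known up to database lock, so state one date rule and apply it to resolved and unresolved occurrences alike.
2. Show the number of unresolved occurrences beside any resolved-only mean and beside its interval table.
3. State the end date used for ongoing events in the cumulative duration.

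The cost is a wording change and one extra descriptive output from AE dates that the planned duration summaries already need. The reported durations may become less favourable. Efficacy analyses, alpha and sample size are untouched.
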